### 3.4.3 Primary Efficacy Endpoints

For Part 1 (Monotherapy Dose expansion) and Part 3 (Combination Dose Expansion), the primary efficacy endpoint is ORR using RECIST 1.1

The point estimates of ORR along with the exact Clopper-Pearson 95% CI will be presented by treatment arm in the Monotherapy Dose Expansion part and Combination Dose Expansion part and overall based on the Efficacy Population.

For Part 2 (Combination Dose Finding), the efficacy analyses are considered as secondary (see Section 3.4.4).

### 3.4.4 Secondary Efficacy Endpoints

#### 3.4.4.1 Tumor response data

##### 3.4.4.1.1 ORR for Part 2 (Combination Dose Finding)

The point estimates of ORR per RECIST 1.1 along with the exact Clopper-Pearson 95% CI will be presented for each arm by dose level in the Combination Dose Finding part based on Efficacy Population.

##### 3.4.4.1.2 iORR

The point estimates of iORR per iRECIST along with the exact Clopper-Pearson 95% CI will be presented by treatment arm in the Monotherapy Dose Expansion part based on the Efficacy Population.

##### 3.4.4.2 BOR, iBOR and tumor burden

The best overall response will be determined according to RECIST 1.1 criteria and according to iRECIST. The BOR/iBOR will be presented for each arm by dose level in the Combination Dose Finding part and by treatment arm in the Monotherapy Dose Expansion part and Combination Dose Expansion part and overall based on the Efficacy Population.

The tumor burden change for patients will be calculated for each patient in the Efficacy Population as the percent change from baseline in the sum of diameters (SoD) of target tumor lesions at each assessment time point based on RECIST 1.1. The best tumor burden change (decrease) will be summarized descriptively.

A waterfall plot of the best percent change (decrease) in SoD from baseline for each subject will be presented. A spider plot of the percent change in SoD from baseline at scheduled post-baseline visits will be presented. A swimmer plot will be used to show the occurrence of clinical outcomes of interest over time (response, progression, treatment duration, death, etc.).

All tumor response data will be listed.

##### 3.4.4.3 Disease Control Rate

DCR per RECIST v1.1 and iDCR per iRECIST will be analyzed in same manner as ORR.

##### 3.4.4.4 Duration Of Response

DOR and iDOR based on the Investigator assessment will be estimated using the Kaplan-Meier method. The Kaplan-Meier estimate of the first quartile, median, and third quartile for DOR and iDOR and the 95% CIs for the median calculated using the Brookmeyer-Crowley method will be

presented. The event-free rate with the 95% CI calculated using Greenwood's formula will be provided for selected time points.

Kaplan-Meier plots of DOR and iDOR will be presented.

#### *3.4.4.5 Progression Free Survival*

Unless specified otherwise, the analytical methods described in Section 3.4.4.3 for DOR/iDOR will be used for PFS/iPFS. PFS/iPFS summaries will be presented based on Safety Population.

In addition, the number and percentages of patients experiencing a PFS/iPFS event, types of events, and patients censored will be summarized.

#### *3.4.4.6 Overall survival*

Unless specified otherwise, the analytical methods described in Section 3.4.4.3 for DOR will be used for OS. OS summary will be presented based on Safety Population.

#### *3.4.4.7 Time To Response*

[figure not shown]
TTR/iTTR will be summarized descriptively by calculating the mean, median, standard deviation, and minimum and maximum values.

### 3.5 Pharmacokinetic Assessments

Pharmacokinetic assessment for this study will be performed by external vendors. The following plan will be applied.

#### *3.5.1 Description of Pharmacokinetic Variables*

Blood samples for the assessment of PK will be taken at the following visits/timepoints:

#### *3.5.2 Pharmacokinetics Evaluation*

The following PK parameters will be estimated by non-compartmental approach using actual elapsed time from dosing for Cycle 1 only.

Following the interim analysis of the first part of the study (Part 1) using a data cut-off of October 17th, 2023, Anaveon has decided to not pursue the development of ANV419 in unresectable or metastatic melanoma. As a result, no pharmacokinetic data were generated after October 17th, 2023.

- $AUC_{0-\text{last}}$ : Area under the concentration-time curve ( $\mu\text{g}/\text{L} * \text{hours}$ ) from time zero (pre-dose) to the last measurable concentration, calculated using the trapezoidal method (as defined in Phoenix WinNonLin manual, Certara)
- $AUC_{0-\infty}$ : Area under the concentration curve ( $\mu\text{g}/\text{L} * \text{hours}$ ) from time zero (pre-dose) to infinity, calculated trapezoidal methods with linear interpolation (as defined in Phoenix WinNonLin manual, Certara) and extrapolated to infinity by addition of the last

quantifiable concentration divided by the elimination rate constant:  $AUC_{0-\text{last}} + C_{\text{last}}/\lambda_z$ . All the data measured will be reported and summarized;

- $\%AUC_{\text{ex}}$ : Percent of the area extrapolated for the calculation of  $AUC_{0-\infty}$ ;
- $C_{\text{max}}$ : Maximum concentration (ng/mL), obtained directly from the observed concentration versus time data;
- $T_{\text{max}}$ : Time to maximum concentration (hours), obtained directly from the observed concentration versus time data;
- $C_{\text{last}}$ : Last measurable concentration (ng/mL), obtained directly from the observed concentration versus time data;
- $T_{\text{last}}$ : Time (hours) of last concentration, obtained directly from the observed concentration versus time data;
- $t_{1/2}$ : half-life (hours), determined as  $\ln(2)/\lambda_z$ ;
- $V_{\text{ss}}$ : volume of distribution at steady state (L), calculated as Dose/ $(AUC_{0-\infty}\lambda_z)$ ;
- $\lambda_z$ : terminal elimination rate constant (1/hours), determined by linear regression of terminal points of the log-linear concentration-time curve. A minimum of three data points are required for determination of  $\lambda_z$ , with an r-square value  $\geq 0.7$ . In addition, visual assessment will be used to identify the terminal linear phase of the concentration-time profile.

For calculations using the trapezoidal rule, the following formula will be used:

$$AUC = \frac{(C_1 - C_2)}{2}(t_2 - t_1)$$

For interpolation the following rule will be used if applicable

$$C^* = C_1 + \left| \frac{t^* - t_1}{t_2 - t_1} \right| (C_2 - C_1)$$

Where  $C^*$  is the concentration at time  $t^*$

Pharmacokinetic data will be reported by Think Q2. Details are included below but these outputs will not be created by Medpace.

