
AE = adverse event; AESI = adverse event of special interest; CD = cluster of differentiation; CR = complete response; ctDNA = circulating tumor deoxyribonucleic acid; DCR = disease control rate; DOR = duration of response; ECG = electrocardiogram; FoxP3 = Forkhead box P3; iCR = immune complete response; iDCR = immune disease control rate; iDOR = immune duration of response; IFNγ = interferon gamma; IL = interleukin; iPFS = immune progression-free survival; iPR = immune partial response; irAE = immune related adverse event; iRECIST = immune Response Evaluation Criteria in Solid Tumors; iSD = immune stable disease; iTTR = immune time to response; ORR = objective response rate; OS = overall survival; PD-1 = programmed death-1; PD-L1 = programmed death-ligand 1; PFS = progression-free survival; PR = partial response; RECIST = Response Evaluation Criteria in Solid Tumors; SAE = serious adverse event; SD = stable disease; T cell = thymus lymphocyte cell; TNF = tumor necrosis factor; TTR = time to response; v1.1 = version 1.1.

Table 3. Study Objectives and Endpoints for Part 2: Combination Dose Finding

Table 3. Study Objectives and Endpoints for Part 2: Combination Dose Finding				
Combination Dose Finding – Combination Therapy Arms (Arms B and C)				
Primary Objectives	Primary Endpoints			
Evaluate the safety and tolerability and determine the RP2D of ANV419 in combination with pembrolizumab	Incidence, frequency, and severity of AEs including the following: - SAEs; - TEAEs; - DLTs;			
Evaluate the safety and tolerability and determine the RP2D of ANV419 in combination with ipilimumab	 AESIs; irAEs; AEs leading to discontinuation of the study; and Changes from baseline in laboratory parameters, vital signs, ECGs, and physical examinations. 			
Secondary Objectives	Secondary Endpoints			
Evaluate PK and PD of ANV419 in combination with	PK endpoints in serum: - CL of ANV419; - V _{ss} of ANV419; - AUC of ANV419; and - C _{max} of ANV419. PD endpoints in peripheral blood: including, but not limited to, CD3, CD4,			
pembrolizumab or ipilimumab	CD8, CD56, CD16, CD25, FoxP3, CD279, and CD366.			
Explore immunogenicity after exposure to ANV419 in combination with pembrolizumab or ipilimumab	Incidence of immunogenicity as indicated by ADA.			

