6.5 Pharmacokinetic Analyses

Serum samples for PK will be drawn as indicated in Appendix A.

If warranted for additional safety assessments, additional samples can be collected by the Investigator after discussion with the Sponsor. All samples will be sent to the central laboratory. Please refer to the laboratory manual for details.

PK parameters to be analyzed:

- Systemic clearance (CL) of ANV419;
- Volume of distribution at steady state (V_{ss}) of ANV419;
- Area under the concentration-time curve (AUC) of ANV419; and
- Maximum observed serum concentration (C_{max}) of ANV419.

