6.6 Pharmacodynamic Analyses (Immuno-Profiling and Ki67 Analysis)

Blood samples for PD will be drawn as indicated in Appendix A.

All samples will be sent to the central laboratory. Please refer to the laboratory manual for details.

Immunophenotyping using flow cytometry has become the method of choice in identifying cells within blood samples and can therefore be used to monitor the mode of action of ANV419 as monotherapy or in combination with other treatments. Potential predictive markers of efficacy will also be explored.

Immunophenotyping markers may include, but will not be limited to, CD3, CD4, CD8, CD25, FoxP3, CD56, CD16, CD279, CD366, and Ki67.

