8.2.8 Analysis of Pharmacodynamics

The result, change, percent change, and maximum percent change in immunologic changes to selected serum cytokines and immune cell subsets in the blood and tumor microenvironment will be summarized descriptively.

PD parameters to be analyzed (including, but not limited to):

• CD3, CD4, CD8, CD56, CD16, CD25, FoxP3, CD279, and CD366.

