Evaluate the safety and tolerability and determine the RP2D of ANV419 in combination with ipilimumab	
PK endpoints in serum:
 
 
- CL of ANV419;
 
- <math>V_{ss}</math> of ANV419;
 
- AUC of ANV419; and
 
- <math>C_{max}</math> of ANV419.
 
 
PD endpoints in peripheral blood: including, but not limited to, CD3, CD4, CD8, CD56, CD16, CD25, FoxP3, CD279, and CD366.

Evaluate PK and PD of ANV419 in combination with pembrolizumab or ipilimumab	
Explore immunogenicity after exposure to ANV419 in combination with pembrolizumab or ipilimumab	Incidence of immunogenicity as indicated by ADA.
Evaluate the efficacy of ANV419 in combination with pembrolizumab or ipilimumab	ORR (CR + PR), as defined by RECIST.

Expand evaluation of efficacy of ANV419 in combination with pembrolizumab or ipilimumab	DOR (per RECIST) and iDOR (per iRECIST) measured from first response until disease progression; PFS, iPFS, and OS; DCR (DCR = CR + PR + SD), iDCR (iDCR = iCR + iPR + iSD), Median TTR; and Median iTTR.
Evaluate clinical benefit in quality of life after exposure to ANV419 in combination with pembrolizumab or ipilimumab	Change in QoL at baseline and every 12 weeks while receiving ANV419 via QoL evaluations: - EQ-5D-5L; and - QLQ-C30.
Exploratory Objectives	Exploratory Endpoints
Explore the changes in the tumor microenvironment before and after adding ANV419 as monotherapy and in combination with pembrolizumab or ipilimumab	
Changes in immunological biomarker expression from baseline and post treatment tumor and liquid biopsies, including:
 
 
Immune cell counts, immunophenotyping (including, but not limited to, CD3, CD4, CD8, CD56, CD16, CD25, FoxP3, CD279, and CD366);
 
Cytokine production (including, but not limited to, IFN<math>\gamma</math>, IL-2, TNF, IL-6, IL-10); and
 
 
Immunohistochemistry (including, but not limited to, CD8, CD4, Ki67).
 
Analysis of mutations in the tumor and analysis of tumor mutational burden.
 
Analysis of changes in baseline ctDNA and at specified timepoints on therapy and after therapy.
 
Analysis of single nucleotide polymorphisms, germline DNA for genome-wide association studies, analysis of T cell receptor repertoire, epigenetic markers, soluble CD25, and soluble PD-1/PD-L1.

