##### 3.1.4 *Summary Statistics*

No formal hypothesis testing is planned, and summaries will in general be descriptive. Appropriate summaries will be provided for each assessment based on data type (continuous or categorical).

Categorical data will generally be summarized with number and percentages of patients. The denominator used for the percentage calculation will be clearly defined. Continuous data will generally be summarized with descriptive statistics including n (number of non-missing values), mean, median, standard deviation, minimum, and maximum.

Time-to-event endpoints (progression-free survival, duration of response, and overall survival) will be summarized using Kaplan-Meier methods and 95% confidence interval.

Unless described otherwise, analyses will in general be presented for each arm by treatment arm and BRAF Mutation status (wild-type or BRAFV600) in the Monotherapy Dose Expansion part and by dose level in the Combination Dose Finding part and Combination Dose Expansion part of, and overall using descriptive statistics.

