### 3.6 Pharmacodynamic Assessments and exploratory Variables

Samples for Pharmacodynamic, biomarkers, and other exploratory samples will be drawn as indicated in the Schedule of Events in the protocol. Except indicated otherwise, Pharmacodynamic analysis will be performed based on the Pharmacodynamic population. Serum cytokines analysis will be performed based on the Safety Population.

The different biomarkers tested by Flow cytometry, as well as serum cytokines are represented in Appendix C. The list presented in the Appendix is an exhaustive list and may be changed depending on the availability of the data and the consent of patients.

The absolute counts per L blood of the immune cell populations determined by flow cytometry will be computed based on the % of each population per lymphocytes. If the parent population is not lymphocytes, the corresponding parent population will be used to calculate the % of each immune cell subpopulation per lymphocytes. The absolute count ( $10^6/L$ ) of each immune cell subpopulation will be calculated based on the determined percentage within lymphocytes and the lymphocytes count determined by Local labs. The different computation equations and populations are represented in Appendix D.

The change in the percentages or absolute values over time and fold change from baseline of selected biomarker will be summarized descriptively. Plots of the absolute values and the Fold change from Baseline will also be presented.

Individual pharmacodynamic and biomarkers data will be listed by patient.

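### SAP 3.5.2 leaves out clearance, one of the four PK parameters the protocol names for analysis, and SAP Section 5 does not declare the change

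*SAP*

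**What the plan says.** **Protocol.** Section 6.5 lists the PK parameters for analysis and begins with "Systemic clearance (CL) of ANV419", followed by Vss, AUC and Cmax. Section 8.2.7 repeats the four and asks for summaries by treatment arm. Neither section is restricted to a study part. The objectives tables are narrower: PK is a secondary endpoint only in Part 2, under the objective that starts "Evaluate PK and PD of ANV419 in combination with".

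**SAP.** Section 3.5.2 states: "The following PK parameters will be estimated by non-compartmental approach using actual elapsed time from dosing for Cycle 1 only". Its list is AUC0-last, AUC0-inf, percent AUC extrapolated, Cmax, Tmax, Clast, Tlast, half-life, Vss and the terminal rate constant (lambda_z). Section 3.5.4, on summarising the parameters, does not add clearance. Clearance survives only in the abbreviation list and in Table 2-2 for Part 2, under "PK endpoints in serum".

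SAP Section 5 declares two changes: all Part 2 and Part 3 analyses are dropped, and so is the Part 1 iRECIST analysis.

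**Biomarkers.** Protocol 8.2.8 names "CD3, CD4, CD8, CD56, CD16, CD25, FoxP3, CD279, and CD366". SAP Table 2-1 keeps these as Part 1 exploratory endpoints, together with cytokine production including IL-2. SAP 3.6 describes its Appendix C in these words: "The list presented in the Appendix is an exhaustive list and may be changed depending on the availability of the data". The appendix contains neither CD279 nor CD366, and its cytokines are serum measurements only.

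**The concern.** A parameter that the protocol says will be analysed has disappeared from the analysis plan, and the section meant for such changes is silent. A reader of the study report could not tell whether clearance was dropped deliberately, overlooked, or computed and left out.

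Clearance has some scientific relevance. Protocol 1.3 describes target-mediated disposition as what mainly drives clearance of ANV419. Protocol 1.3.2 reports faster apparent elimination at lower doses in monkeys. Part 1 randomises patients to two doses, so clearance by arm would be a natural descriptive summary of whether the same pattern appears in patients.

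**Working it through.** No sample size, power or error rate is involved. The check compares lists and then asks whether the missing quantity can be recovered.

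**1. PK lists**

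| Protocol 6.5 and 8.2.7 | SAP 3.5.2 |
|---|---|
| CL | absent |
| Vss | present |
| AUC | present (AUC0-last, AUC0-inf) |
| Cmax | present |

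One of four is missing.

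**2. Does dropping Part 2 explain it?** No. Vss, AUC and Cmax sit beside CL in the same Part 2 endpoint tables (Protocol Table 3, SAP Table 2-2), yet SAP 3.5.2 keeps those three. That section covers Part 1 data, since it cites the Part 1 interim cut-off of 17 October 2023. Part 1 PK sampling is set out in the notes to Protocol Table 20. Removing Part 2 would account for losing all four parameters, but not for losing one.

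**3. Can CL be computed from what is kept?** Yes. After intravenous dosing, CL = Dose/AUC0-inf. SAP 3.5.2 derives AUC0-inf and already uses Dose in its volume formula, Dose/(AUC0-inf × lambda_z). With dose in mcg (SAP 3.3.8) and AUC in µg/L × hours, CL comes out in L/hour. Because of how the SAP writes its volume, lambda_z times that volume gives the same CL. Two illustrations with assumed values:

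- One compartment, Dose 1000, V 5, k 0.05: AUC0-inf = 1000/(5 × 0.05) = 4000. CL = 1000/4000 = 0.25. SAP volume = 1000/(4000 × 0.05) = 5, and 0.05 × 5 = 0.25.
- Two compartments, Dose 1000, coefficients 150 and 50, rates 0.5 and 0.05: AUC0-inf = 150/0.5 + 50/0.05 = 1300. CL = 1000/1300 = 0.769. SAP volume = 1000/(1300 × 0.05) = 15.4, and 0.05 × 15.4 = 0.77, which is 0.769 before rounding.

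**4. Is the AUC safe to use?** Not as printed. The trapezoid formula at the end of SAP 3.5.2 uses (C1 − C2)/2 × (t2 − t1); the rule requires (C1 + C2). For an assumed fall from 100 to 60 over 2 hours, the printed form gives (100 − 60)/2 × 2 = 40 and the correct form (100 + 60)/2 × 2 = 160. Any CL based on the printed formula would carry that error.

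**5. Biomarker lists.** Of the nine markers in Protocol 8.2.8, seven appear in SAP Appendix C; CD279 and CD366 do not. Protocol 6.8 places IL-2 among cytokines measured in PBMC samples, along with interferon gamma, TNF, IL-6 and IL-10. The SAP has no analysis of that PBMC readout. These three items cannot be derived from anything in SAP Appendices C or D.

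**The case against.** The case for leaving the SAP alone has several good parts.

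- **Clearance is not a Part 1 endpoint.** The Part 1 objectives tables contain no PK endpoint, and Section 5 openly removes Part 2, where CL is one. Protocol 8.2.7 also speaks of calculating selected parameters and of summaries where appropriate, which leaves some latitude. A reader might infer that nothing permits dropping CL; that goes too far. What stands is that both protocol sections name CL individually, and the SAP keeps its three companions without explaining why it goes.
- **The data are not lost.** A reader might infer that clearance cannot be reported. Step 3 shows that it can.
- **The pharmacology is not unmeasured.** It is tempting to say that dose-dependent elimination is left with no measurement. AUC0-inf, half-life and lambda_z by dose level all bear on it, and no objective sets a clearance comparison between the two arms.
- **The biomarkers are optional.** Protocol 6.6 is permissive: "Immunophenotyping markers may include, but will not be limited to, CD3, CD4, CD8, CD25, FoxP3, CD56, CD16, CD279, CD366, and Ki67". Protocol 6.10 lets the sponsor omit biomarker collection or analysis, and SAP 3.6 says its list may change. This stands, and it reduces that item to record-keeping. The discretion in 6.10 concerns biomarkers, so it does not reach CL.
- **IL-2 is not missing from a serum panel.** A reader might count one of five named cytokines as absent. Protocol 8.2.8 names no individual cytokine, and the five belong to the PBMC production readout. Adding IL-2 to the serum list would therefore close nothing.
- **Little depends on the outcome.** The SAP says "No formal hypothesis testing is planned, and summaries will in general be descriptive", and the trial stopped after Part 1 with no responses. This limits the severity.

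**Conclusion.** The point holds as a minor one. Clearance is one of four PK parameters that the protocol names for analysis, it is absent from SAP 3.5.2, and Section 5 does not declare its removal. It has been omitted but is still obtainable. No test, endpoint of the analysed part or stopping decision depends on it.

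This rests on reading Protocol 6.5 and 8.2.7 as applying to Part 1, which their wording and the SAP's own Part 1 PK list support. It also assumes that AUC0-inf can be estimated. In patients whose terminal phase fails the SAP's conditions (at least three points and an r-square of at least 0.7), CL will be unavailable, as AUC0-inf itself will be.

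The trapezoid formula may be only a typographical slip, because SAP 3.5.2 also refers to the PK software manual for the method. The documents do not show which was applied, so it should be confirmed.

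The biomarker discrepancy is real within the SAP (Table 2-1 against Section 3.6 and Appendix C) but is housekeeping: exploratory in Part 1 and open to omission by the sponsor.

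**What to change.** 1. In SAP 3.5.2, add CL = Dose/AUC0-inf (L/hour), using the Cycle 1 dose actually given, and summarise it by arm with the other parameters. Show it next to percent AUC extrapolated.
2. Correct the printed trapezoid to (C1 + C2)/2 × (t2 − t1), and confirm with the external PK vendor which formula was used, before any CL is derived.
3. In SAP Section 5, state for Part 1 whether CD279, CD366 and PBMC cytokine production (including IL-2) were measured and analysed. If they were, add them to the SAP's analysis lists; if not, say so.

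The cost is a few lines of SAP text and one derived variable from the vendor. CL needs no new samples or data. If the database is already locked, SAP Section 1 provides for recording the change in the clinical study report.

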1.3 ANV419

ANV419 is being developed by Anaveon AG for the treatment of multiple advanced solid tumors and multiple myeloma as a single agent and in combination with other immunostimulatory approaches. ANV419 is a stable fusion protein comprised of IL-2 fused to an anti-IL-2 monoclonal antibody (mAb) that sterically blocks the binding of the IL-2 to IL-2R alpha (α) chain. As a result, ANV419 is a high molecular weight IL-2 agonist which signals through the IL-2R β/γ present on NK cells and CD8+ T cells but shows markedly reduced signaling through the IL-2R $\alpha/\beta/\gamma$ present on Tregs. ANV419 has a longer half-life relative to IL-2, shows good selectivity towards the expansion of NK and CD8+ T cells over Tregs, in the ongoing ANV419-001 Phase 1 study. In addition, the covalent linkage to IgG prolongs the half-life of ANV419, leaving target mediated disposition as the major driver of clearance. Compared with other novel IL-2 agents, the molecular characteristics of ANV419 aim to enable delivery of a higher molar equivalent of IL-2, with improved tolerability and safety profile, combined with a long duration of action, resulting in effective therapy in an outpatient setting.

Available data for ANV419 support the hypothesis that it may potentially provide a favorable risk/benefit profile for patients with cancer, who can benefit from immunotherapy.

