1.3.2 Nonclinical Pharmacokinetics

The pharmacokinetic (PK) behavior of ANV419 was characterized in cynomolgus monkeys following IV bolus administration and the serum concentration-time profiles were analyzed using
population PK modeling. A non-linear and faster apparent elimination of ANV419 from serum at
lower doses/concentrations was observed, consistently with a target-mediated drug disposition phenomenon.

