- t. Female patients of childbearing potential must have a negative serum pregnancy test at the Screening Visit and negative (urine or serum) pregnancy test within 72 hours prior to study Day 1. If the urine test is positive or cannot be confirmed negative, a serum pregnancy test will be required and must be negative for the patient to be eligible.
- u. Imaging performed prior to signing consent can be used for screening purposes if done within 8 weeks from signing consent. Baseline disease assessment using CT imaging (including brain assessment) is to be performed within 21 days of baseline.
- v. CT scan is not required at EOS if available within 4 weeks prior to the EOS Visit.
- w. If warranted for additional safety assessments, additional samples can be collected by the Investigator after discussion with the Sponsor. For patients who discontinue for reasons other than progressive disease, PK/ADA samples will be collected during post-treatment follow-up disease status until disease progression.
- x. To be collected pre-dose and then 2 (± 30 minutes) and 4 hours (± 1 hour) post end of infusion of ANV419.
- y. PK samples to be drawn pre-dose and then 15 minutes (±5 minute), 1 hour (±30 minutes), 2 hours (±30 minutes), 4 hours (±1 hour), and 8 hours (±1 hour) post end of infusion.

- z. PK samples to be drawn 24 hours (± 1 hour) post end of infusion.
- aa. PK samples to be drawn 72 hours (±1 hour) post end of infusion.
- bb. PK samples to be drawn pre-dose and then 1 hour (±30 minutes), and 2 hours (±30 minutes) post end of infusion.
- cc. Samples to be drawn pre-dose.
- dd.
- ee. All ADA samples to be taken pre-dose. Additional samples will be taken in the case of an IRR or irAE to rule out involvement of ADA.
- ff. If warranted for an additional PD assessment or if a PD visit is missed, an additional blood sample can be collected by the Investigator at a later visit after discussion with the Sponsor.
- gg. To be drawn
- hh. Tumor biopsies for research purpose may be performed within ± 3 days of the imaging assessment and within 7 days of the start of the dosing cycle if deemed safe and clinically feasible. Any tissue that is suspected to contain tumor, including lymph nodes, may be biopsied. All biopsies are optional.
- ii. Acetaminophen 1 g may be given to the patients as pre-medication or following the ANV419 infusion and can be used every 8 hours as needed.
- jj. A treatment interval of at least 12 days is required.

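### SAP 3.5.2 gives the formula for the terminal-phase volume (Vz) under the name Vss

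*SAP*

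**What the plan says.** Protocol section 6.5 lists "Volume of distribution at steady state (V_{ss}) of ANV419" among the PK parameters to be analysed, and section 8.2.7 repeats it. Neither section limits it to one study part.

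SAP section 3.5.2 gives the working definition: "volume of distribution at steady state (L), calculated as Dose" over the product of AUC0-∞ and λz. The same list defines λz as the "terminal elimination rate constant (1/hours), determined by linear regression of terminal points of the log-linear concentration-time curve", and AUC0-∞ as AUC0-last plus Clast/λz. The visible list contains no AUMC and no mean residence time. Parameters are estimated for Cycle 1 only and, under SAP section 3.5.4, are listed and summarised descriptively.

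On disposition, protocol section 1.3 describes the link to IgG as "leaving target mediated disposition as the major driver of clearance". Section 1.3.2 reports, in monkeys, "A non-linear and faster apparent elimination of ANV419 from serum" at lower doses and concentrations.

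**The concern.** The label and the formula on the Vss line describe different quantities. Vss relates the amount in the body to the serum concentration at steady state. Dose/(AUC0-∞ × λz) relates them during the terminal phase, and so depends on how fast the drug is eliminated as well as on how it distributes. Both are in litres, so a unit check would not show the mismatch.

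At stake is a wrongly named parameter in the PK report. A reader comparing it with a Vss from another study, or using it as a Vss in later modelling, would be using a different quantity. The consequence inside this trial is small. PK is an endpoint only in Part 2 (protocol Table 3), and SAP section 5 drops all Part 2 and Part 3 analyses. No decision rule and no other visible analysis uses Vss.

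**Working it through.** The documents state no volume, so there is no figure to reproduce. The check is an identity, followed by illustrations under assumed kinetics.

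**Identity**

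- CL = Dose/AUC0-∞.
- SAP expression: Dose/(AUC0-∞ × λz) = CL/λz = Vz.
- Non-compartmental Vss = CL × MRT, with MRT = AUMC0-∞/AUC0-∞ − Tinf/2 for an infusion of length Tinf.
- Ratio: (CL/λz)/(CL × MRT) = 1/(λz × MRT). This is 1 by definition only for a linear one-compartment profile.

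**Worked example** (assumed values; bolus limit): dose 1000, V1 = 3 L, k10 = 0.05, k12 = 0.05, k21 = 0.1 per h.

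- The exponents are 0.1707 and 0.02929 per h, each with coefficient 166.67.
- AUC = 166.67/0.1707 + 166.67/0.02929 = 6,667, so CL = 1000/6,667 = 0.15 L/h.
- AUMC = 166.67/0.1707² + 166.67/0.02929² ≈ 200,000, so MRT = 200,000/6,667 = 30 h.
- CL × MRT = 0.15 × 30 = 4.50 L, which equals the true value V1(1 + k12/k21) = 3 × 1.5.
- SAP expression: 0.15/0.02929 = 5.12 L. The ratio is 1.14.

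The same calculation with other assumed constants and V1 = 3 L:

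| k10, k12, k21 (per h) | SAP expression (L) | Vss (L) | Ratio |
|---|---|---|---|
| one compartment, k10 = 0.05 | 3.00 | 3.00 | 1.00 |
| 0.05, 0.05, 0.1 | 5.12 | 4.50 | 1.14 |
| 0.1, 0.1, 0.05 | 13.69 | 9.00 | 1.52 |
| 0.2, 0.1, 0.03 | 31.07 | 13.00 | 2.39 |

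**As the SAP would estimate it**

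Sampling times come from protocol Table 20, footnotes y, z and aa: "PK samples to be drawn pre-dose and then 15 minutes (±5 minute), 1 hour (±30 minutes), 2 hours (±30 minutes), 4 hours" and 8 hours, then "PK samples to be drawn 24 hours (± 1 hour) post end of infusion" and "PK samples to be drawn 72 hours (±1 hour) post end of infusion". Further assumptions:

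- These times form the whole Cycle 1 profile, with no BLQ values.
- The infusion lasts 15 minutes. That figure stands in the combination dose table; the Part 1 duration is not visible.
- AUC is by linear trapezoid plus Clast/λz, and λz is fitted to the last three points. The lowest r-square was 0.94, above the SAP's limit of 0.7.

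*Linear two-compartment grid*: k10 0.02, 0.05, 0.1, 0.2; k12 0.05, 0.1, 0.2; k21 0.1, 0.2, 0.4 per h; 4 × 3 × 3 = 36 combinations.

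| Ratio | Range | Median |
|---|---|---|
| Exact Vz / Vss, no sampling error | 1.01 to 1.85 | 1.07 |
| Printed expression / (CL × MRT), same samples | 1.01 to 1.67 | 1.16 |
| Printed expression / true Vss | 0.87 to 1.42 | 0.98 |
| CL × MRT / true Vss | 0.77 to 0.96 | 0.84 |

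*Saturable elimination*: Vmax/Km 0.1 per h; C0/Km 0.1, 1, 3, 10; k12 = 0 or 0.1, k21 = 0.2; 8 cases. The printed expression divided by CL × MRT is 0.88 to 1.23. Against true Vss, the printed expression gives 0.53 to 0.94 and CL × MRT gives 0.58 to 0.89.

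**Two smaller points to check**

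- The trapezoid in SAP 3.5.2 appears as half the difference C1 − C2 times the interval. Integrating the SAP's own interpolation rule from t1 to t2 gives (C1 + C2)/2 × (t2 − t1). The minus may come from reading the PDF by program.
- CL is listed in protocol sections 6.5 and 8.2.7 but has no line in SAP 3.5.2. It may be in SAP 3.5.1, whose content is not visible.

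**The case against.** The strongest objection is that the usual alternative is no more accurate here. With gaps from 8 to 24 to 72 hours and a linear trapezoid, CL × MRT underestimates true Vss throughout the linear grid, and the printed expression is nearer the truth in 31 of the 36 combinations. Under saturable elimination neither recovers it. This stands. It means the finding cannot be put as a bias that CL × MRT would cure, and it favours relabelling. It does not make the label right: the printed expression is often close because sampling error offsets the definitional gap, under kinetics that were assumed.

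The 1.16 median also overstates the definitional gap, because its comparator is biased low; without sampling error the median on the same grid is 1.07. That too is right.

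A third objection is that PK software would return the correct Vss anyway. SAP 3.5.2 defers to the software manual only for the AUC lines, and the Vss line carries its own formula. If the software output departed from it, the SAP and the report would disagree.

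Finally, Part 1 has no PK endpoint and the formula is printed in full for any reader to see. That limits the severity. However, SAP section 5 does not drop Part 1 PK, so the mislabelled values can still be reported.

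**Conclusion.** The label is wrong as written: SAP 3.5.2 would report Vz as Vss. This rests on the algebra alone and is certain. How far the two differ for ANV419 cannot be derived from the documents. The ratios found, 1.01 to 1.67 in the linear cases and 0.88 to 1.23 in the saturable ones, depend on assumed rate constants, infusion time and sampling profile, and even the direction is not fixed. The finding is minor. It touches descriptive Cycle 1 PK from Part 1, and leaves ORR and the decision to stop unchanged. The trapezoid sign and the missing CL line are questions to settle against the full SAP, not established errors.

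**What to change.** In SAP section 3.5.2, do one of the following:

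- Relabel the printed expression Vz, and record in SAP section 5 that the protocol-listed Vss is not reported. This is preferable, because AUMC is poorly determined on this sampling schedule.
- Define Vss = CL × MRT, with CL = Dose/AUC0-∞ and MRT = AUMC0-∞/AUC0-∞ minus half the infusion time, and state its limits under sparse sampling and non-linear elimination.

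Also check the trapezoid sign in the original PDF and, if it is a minus, correct it to (C1 + C2)/2 × (t2 − t1). Confirm whether SAP 3.5.1 derives CL; if not, add CL = Dose/AUC0-∞.

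The cost is a change of wording. All these quantities come from the same concentrations, doses and times, so no new data are needed.
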